2.3.1 Risk Assessment Table 2	Editorial changes to clarify Impaired wound healing and embryofetal toxicity as an important potential risk for bintralusp alfa	Editorial changes for clarification.
6.9 Special Precautions	The section has been merged into Section 7.1	Changes are made to align with the current protocol template.
7.1 Discontinuation of Study Intervention	Discontinuation of study intervention for participants from Study MS200647_0005 is clarified.	Discontinuation of study intervention is as specified in the parent protocol for participants from MS200647_0005.
8.3.6.2 Immune-related Adverse Events	Immune related pneumonitis has been added For some conditions like endocrinopathies, hepatitis action to be taken on study treatment has been deleted.	The missing event has been added to complete list of irAEs. Information has been deleted to maintain consistency across protocols for the bintralusp alfa.

Section # and Name	Description of Change	Brief Rationale
8.3.6.5 Bleeding Adverse Events	Guidance has been provided on bintrafusp alfa dose modification/interruption when Grade ≥ 3 bleeding event and rapid decrease in hemoglobin is observed during the study.	The dose modification/interruption guideline will help Investigator to ensure participants safety during the study.
8.3.7 Other Important Potential Risks	The section has been deleted as information is already presented in Section 2.3.1	Information is already presented in Section 2.3.1 Risk Assessment. Therefore, text has been deleted from Section 8.3.7.
8.4 Treatment of overdose	The definition of overdose is clarified	To clarify overdose.
11 Appendices Clinical laboratory tests	Free T4 and TSH tests are removed from the list of tests at Screening	To align with schedule of activities table as these tests to be done during Treatment Phase.

Note: Minor changes have been performed throughout the protocol to address consistency pertaining to major changes done in the protocol or to add further clarity and precision.

Free T4 = free thyroxine; TSH = thyroid-stimulating hormone; irAEs = Immune-related adverse events

- Confidential -

1.1 Synopsis

Protocol Title: An Open-label, Multicenter Follow-up Study to Collect Long-term Data on Participants from Multiple Bintralusp alfa (M7824) Clinical Studies

Short Title: Bintralusp alfa Program Rollover Study

CCI

Objectives and Endpoints:

Objectives	Endpoints
Primary	
To evaluate clinical safety of bintralusp alfa in participants with solid tumors who continue treatment after completion of the primary/main analyses in parent bintralusp alfa studies	Occurrence of AEs and treatment-related AEs, starting from baseline in parent study
Secondary	
To evaluate clinical efficacy of bintralusp alfa based on OS	OS, starting from baseline in parent study

CCI

Abbreviations: AE=Adverse Events; CCI CCI OS=Overall survival, RECIST=response evaluation criteria for solid tumors.

Overall Design: This is a Phase III, open-label, multicenter, rollover study designed to provide participants from parent bintralusp alfa studies with continuous access to bintralusp alfa, to monitor the safety and tolerability of bintralusp alfa, and to collect long-term efficacy and safety data. Participants in a parent bintralusp alfa study where the primary/main analysis has been completed or after discontinuation of study before primary/main analysis has been completed will be eligible for enrollment in the rollover study. Specifically, the following participants will be eligible for enrollment in this rollover study:

- Participants who are currently on active bintrafusp alfa treatment (alone as a monotherapy or following discontinuation of other combination treatment agents) in an eligible parent study without treatment interruption at the time of rollover study enrollment.
- Participants who:
 - Achieved confirmed complete response (CR), partial response (PR), or stable disease (SD) in an eligible parent study
 - Discontinued bintrafusp alfa treatment according to the parent study protocol
 - Subsequently developed disease progression
 - Are willing to re-start bintrafusp alfa treatment deemed potentially beneficial by the participants' physicians.
- Participants who:
 - Discontinued from bintrafusp alfa treatment in an eligible parent study due to an AE(s) that was subsequently well managed or resolved after stopping therapy
 - And are willing to re-start bintrafusp alfa treatment if deemed potentially beneficial by the participants' physicians and provided that the parent study protocol permits reinitiation of bintrafusp alfa if a participant discontinued treatment due to toxicity.

Note: Participants who have had AEs requiring permanent treatment discontinuation, like certain immune-related adverse events (irAEs) or certain bleeding events are excluded from participation in the rollover study.

Participants can be transferred from their respective parent bintrafusp alfa study to this rollover study once the primary/main analysis in the parent study has been completed or after discontinuation of study before primary/main analysis has been completed. Participants may also be transferred upon Sponsor decision in case the parent study is terminated for any reason as specified in the parent study protocol and there is a medical need for participants to continue to be treated with bintrafusp alfa that cannot be otherwise supplied. The final decision whether to transfer participants from the parent study rests with the Sponsor.

Brief Summary:

Brief Summary:

This study is designed to provide continuous access to treatment with bintrafusp alfa for eligible participants from ongoing bintrafusp alfa parent studies, and to collect long-term safety and efficacy data:

- Study Duration: All participants in this rollover study will be treated with bintrafusp alfa until meeting defined criteria in the initial study protocol (parent) for discontinuation, until study intervention is commercially accessible and provisioned via marketed product, or until end of study. The study also includes a 5 years survival follow-up after last dose of the study treatment.
- Treatment Duration: Treatment under the rollover protocol according to the interval and dosing schedule in the parent protocol until discontinuation.
- Treatment Frequency: 1200 mg once every 2 weeks; 2400 mg once every 2 weeks; 2400 mg once every 3 weeks. Other dose amount as specified in the participant's parent protocol: once every 2 weeks.
- Bintrafusp alfa is not available through an expanded access program.

Number of Participants: The maximum number of participants who can enter from parent studies is not limited and is dependent on the number of eligible participants from the parent studies. Based on the current status of participants in the ongoing bintrafusp alfa parent studies, it is estimated that at least 10 participants will enter this study (as of April 2021 eCRF data).

Study Intervention Groups and Duration: This is an open-label, single arm study.

[figure not shown]
The study includes:

- Treatment with bintrafusp alfa until disease progression per RECIST v1.1, clinical deterioration, unacceptable toxicity, or any other criterion for withdrawal from study intervention or study is fulfilled.
- In the case of progressive disease, treatment may continue if the participant's performance status (PS) has remained at least stable in the opinion of the Investigator, the participant will benefit from continued treatment, in the opinion of the Investigator and if other criteria are fulfilled as outlined in the protocol.
- Participants who have experienced a confirmed CR should continue treatment for a maximum of 24 months after confirmation of response (at the discretion of the Investigator). If the Investigator believes that a participant with confirmed CR may benefit from treatment beyond 24 months, it may be permissible to continue treatment after discussion with the Medical Monitor and the Sponsor's Medical Responsible.
- Participants with SD or PR who are receiving bintrafusp alfa should continue treatment until meeting criteria for discontinuation.

- Safety Follow-up will continue until 90 days after the last dose of bintrafusp alfa. The 90-day Safety Follow-up is allowed to be conducted via telephone calls unless there is medical necessity requiring a clinical visit.
- Long-term Follow-up should be performed every 12 weeks after the Safety Follow-up according to the Schedule of Activities. Long-term Follow-up should be performed telephone calls unless there is medical necessity requiring a clinical visit
- Survival Follow-up will continue until a maximum of 5 years after the last participant receives the last dose of bintrafusp alfa. This duration may be shortened at the discretion of the Sponsor for any given indication.

Involvement of Special Committee(s): No

1.2 Schema

^aParticipants in eligible parent studies who discontinued treatment due to confirmed CR, PR, or SD, subsequently developed disease progression or due to an AE(s) that is subsequently well managed or resolved after stopping therapy are eligible for enrollment in order to reinitiate treatment with bintralusp alfa in the rollover study, as permitted by the parent study protocol.

^b Informed consent may be obtained during the last scheduled treatment visit of the parent study, provided that the participant is on active treatment in the parent study at the time of the visit. Informed consent will be obtained during Eligibility Visit of the rollover study from participants who discontinued treatment due to confirmed CR, PR, or SD, subsequently developed disease progression or due to an AE(s) in eligible parent studies.

^c In the case of progressive disease, treatment may continue if the participant's performance status (PS) has remained at least stable in the opinion of the Investigator, the participant will benefit from continued treatment, in the opinion of the Investigator and if other criteria are fulfilled as outlined in the protocol (see [Section 7.1.2](#)).

^d Overall survival and post-treatment anticancer therapies data collection will continue for all participants. For participants without disease progression at the time of rollover or treatment discontinuation, tumor assessment data collection will continue until PD or until 30 days after end of treatment with bintralusp alfa, whichever is later. For details on reinitiating course of treatment refer to [Section 6.7](#)

1.3 Schedule of Activities

The Schedule of Activities is presented in [Table 1](#).

Table 1 Schedule of Activities

Assessments and Procedures	Eligibility Visit	Treatment Phase	End of Treatment	Safety Follow-up		Long-term Follow-up	Notes
	Day -28 to -1	Day 1 Until Discontinuation of Treatment (\pm 3 days); See Notes	See Notes	Visit 30 Days After Last Treatment (\pm 5 days)	Phone Call 90 Days After Last Treatment (\pm 5 days)	Phone Call Every 12 weeks (\pm 2 weeks)	
Treatment Phase: Participants entering this rollover study on active treatment with bintralusp alfa in a parent study should begin Day 1 treatment under the rollover protocol according to the interval and dosing schedule in the parent protocol.
 
End of Treatment: Visit should be held within 30 days of last treatment for participants discontinuing due to AEs. For all others, visit should be held within 7 days of last treatment or prior to any new antineoplastic therapy, whichever is earlier.

Informed Consent	X						
If the participant is on active treatment in the parent study, informed consent can be obtained during the last scheduled treatment visit of the parent study.
 
Informed consent will be obtained during Eligibility Visit of the Rollover study from participants who discontinued due to confirmed CR, PR, or SD, subsequently developed disease progression or due to an AE(s) in eligible parent studies.

Inclusion/Exclusion Criteria	X						
Enrollment	X						Enrollment (if eligible) after fulfilling Inclusion/Exclusion Criteria (see Section 5.1 and Section 5.2).
Physical Exam		According to SOC and institutional guidelines					
Vital Signs							
ECOG PS							

Assessments and Procedures	Eligibility Visit	Treatment Phase	End of Treatment	Safety Follow-up		Long-term Follow-up	Notes
	Day -28 to -1	Day 1 Until Discontinuation of Treatment (\pm 3 days); See Notes	See Notes	Visit 30 Days After Last Treatment (\pm 5 days)	Phone Call 90 Days After Last Treatment (\pm 5 days)	Phone Call Every 12 weeks (\pm 2 weeks)	
Treatment Phase: Participants entering this rollover study on active treatment with bintralusp alfa in a parent study should begin Day 1 treatment under the rollover protocol according to the interval and dosing schedule in the parent protocol.
 
End of Treatment: Visit should be held within 30 days of last treatment for participants discontinuing due to AEs. For all others, visit should be held within 7 days of last treatment or prior to any new antineoplastic therapy, whichever is earlier.

Pregnancy test		Day 1 of every other cycle		X			The β -hCG pregnancy test should be determined from either a urine or serum sample according to local practice.
Skin assessment	X	Every 6 weeks	X	X			See Section 8.3.6.3.
Weight		Participants on mg/kg dosing: Day 1 of each cycle; Participants on flat dose: according to SOC					Cycle length determined based upon treatment cycle duration from parent protocol. For participants continuing to receive bintralusp alfa doses based on their weight (mg/kg dosing), body weight should be determined prior to bintralusp alfa administration.
Height	X						
ECG		According to SOC and institutional guidelines					
Hematology							See Section 8.2.4 and Appendix 6 for further details. Blood samples must be drawn prior to dosing and results of selected laboratory tests (see Appendix 6) must be reviewed within 3 days prior to dosing.
Biochemistry							
Urinalysis							
Free T4 and TSH		Every 6 weeks		X			

Assessments and Procedures	Eligibility Visit	Treatment Phase	End of Treatment	Safety Follow-up	Long-term Follow-up	Notes
	Day -28 to -1	Day 1 Until Discontinuation of Treatment (\pm 3 days); See Notes	See Notes	Visit 30 Days After Last Treatment (\pm 5 days)	Phone Call 90 Days After Last Treatment (\pm 5 days)	
Treatment Phase: Participants entering this rollover study on active treatment with bintralusp alfa in a parent study should begin Day 1 treatment under the rollover protocol according to the interval and dosing schedule in the parent protocol.
 
End of Treatment: Visit should be held within 30 days of last treatment for participants discontinuing due to AEs. For all others, visit should be held within 7 days of last treatment or prior to any new antineoplastic therapy, whichever is earlier.

Viral serology (HIV)	As clinically indicated in participants with a history of HIV infection					See Appendix 6 for details. Not required for all participants. Only applicable for participants with a history of HIV. Participants must be adequately consented per local regulations for any HIV-related testing.
Viral serology (HBV and HCV)	As clinically indicated in participants with a history of HBV or HCV infection					See Appendix 6 for details.
Tumor evaluation/staging	X	Until PD or until 30 days after end of treatment with bintralusp alfa, whichever is later, OR according to SOC and institutional guidelines			
For participants reinitiating bintralusp alfa treatment at study entry (or reinitiating treatment after treatment discontinuation in the rollover study; see Section 7.1.2), a rebaseline scan must be performed prior to treatment. For participants entering this rollover study on active treatment with bintralusp alfa, the baseline assessment from the parent study will be used for progression determination (see Section 8.1.1) and therefore imaging is not required during the Eligibility Visit.
 
Tumor response assessments by CT scan or MRI will be performed according to site SOC/institutional guidelines (see Section 8.1.1). For treatment beyond disease progression, see Section 7.1.2.
 
The tumor response assessments will be performed according to RECIST v1.1
	

Assessments and Procedures	Eligibility Visit	Treatment Phase	End of Treatment	Safety Follow-up		Long-term Follow-up	Notes
	Day -28 to -1	Day 1 Until Discontinuation of Treatment (\pm 3 days); See Notes	See Notes	Visit 30 Days After Last Treatment (\pm 5 days)	Phone Call 90 Days After Last Treatment (\pm 5 days)	Phone Call Every 12 weeks (\pm 2 weeks)	
Treatment Phase: Participants entering this rollover study on active treatment with bintralusp alfa in a parent study should begin Day 1 treatment under the rollover protocol according to the interval and dosing schedule in the parent protocol.
 
End of Treatment: Visit should be held within 30 days of last treatment for participants discontinuing due to AEs. For all others, visit should be held within 7 days of last treatment or prior to any new antineoplastic therapy, whichever is earlier.

OS and post-treatment anticancer therapies				X	X	X	Survival information (including assessment of any further anticancer therapy) will be collected every 12 weeks (\pm 2 weeks) up to the end of the study (see Section 4.4).
Premedication (optional) and study intervention administration		Day 1 of each cycle					
See Section 6.5.2 and Section 8.3.6 for premedication information
 
Participants on bintralusp alfa will continue treatment until disease progression, unacceptable toxicity, or study withdrawal (see Section 7).
 
Cycle length determined based upon treatment cycle duration from the parent protocol.

Documentation of AEs	X	X	X	X	X		See Section 8.3 and Appendix 4 for safety recording and reporting. The Safety Follow-up and Long-term Follow-up visits may be conducted by telephone calls as necessary, unless there is a medical necessity requiring a clinical visit.
Concomitant medications	X	X	X	X			

AE = adverse event; β -hCG = beta-human chorionic gonadotropin; CR=complete response, CT = computed tomography; ECG = electrocardiogram; ECOG

PS = Eastern Cooperative Oncology Group Performance Status; HBV = hepatitis B virus; HCV = hepatitis C virus; HIV = human immunodeficiency virus;

MRI = magnetic resonance imaging; OS = overall survival; PD = progressive disease; PR = partial response, RECIST = Response Evaluation Criteria in Solid Tumors version 1.1; SD = stable disease, SOC = standard of care; Free T4 = free thyroxine; TSH = thyroid-stimulating hormone.

2 Introduction

Bintrafusp alfa (M7824) is an innovative first-in-class bifunctional fusion protein composed of the extracellular domain of the human transforming growth factor β (TGF β) receptor II (TGF β RII or TGF β Trap) covalently linked via a flexible linker to the C-terminus of each heavy chain of an immunoglobulin G1 (IgG1) antibody blocking programmed death-ligand 1 (anti-PD-L1). Bintrafusp alfa is currently in clinical development with multiple ongoing Phase I to III clinical studies, in which bintrafusp alfa is being investigated as a monotherapy or in combination with other anticancer treatments in participants with different types of malignancies.

Detailed information on the chemistry, pharmacology, efficacy, and safety of bintrafusp alfa is in the Investigator's Brochure (IB).

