8.2 Safety Assessments and Procedures

The safety profile of the study intervention will be assessed through the recording, reporting and analysis of baseline medical conditions, AEs, physical examination findings, vital signs, ECGs, and laboratory tests. The baseline status and medical history of the participant is assessed at the baseline of the respective parent study.

Comprehensive assessment of any potential toxicity experienced by each participant will be conducted starting when the participants give informed consent and throughout the study. The Investigator will report any AEs, whether observed by the Investigator or reported by the participant; the reporting period is specified in [Section 8.3.1](#).

The safety assessments will be performed according to the SoA ([Table 1](#)). Periodic evaluations of the study data will be conducted by the study team to ensure safety and the validity and scientific merit of the study (see [Section 8.2](#)).

Ongoing events at the 12-week Safety Follow-up visit should continue to be monitored and documented until resolution or resolution with sequelae. All SAEs ongoing at the End of Treatment visit must be monitored and followed up by the Investigator until stabilization or until the outcome is known, unless the participant is documented as "lost to follow-up". Reasonable attempts to obtain this information must be made and documented. It is also the responsibility of

the Investigator to ensure that any necessary additional therapeutic measures and follow-up procedures are performed.

If a liver function test is elevated in a Hepatitis B virus (HBV) or Hepatitis C virus (HCV) positive participant, HBV DNA or HCV ribonucleic acid (RNA) must be monitored to exclude the possibility of reactivation of viral hepatitis. In case of viral reactivation, follow the HBV and HCV management guidelines.

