8.2.4 Clinical Safety Laboratory Assessments

- Blood and urine samples will be collected for the clinical laboratory tests listed in [Appendix 6](#) at the time points listed in the SoA ([Table 1](#)). All samples will be clearly identified.

-
- Additional tests may be performed at any time during the study, as determined necessary by the Investigator or required by local regulations.
 - The tests will be performed by the local laboratory.

The Sponsor will receive a list of the local laboratory normal ranges before shipment of study intervention(s). Any changes to the ranges during the study will be forwarded to the Sponsor or designated organization.

The Investigator will review each laboratory report, document this review, and record any clinically relevant changes occurring during the study in the AE section of the CRF. The laboratory reports will be filed with the source documents.

8.3

Adverse Events and Serious Adverse Events

The definitions of an AE and a SAE are in [Appendix 4](#) Adverse Events: Definitions and Procedures for Recording, Evaluating, Follow-up and Reporting.

The Investigator and any qualified designees (e.g., Sub-Investigators) are responsible for detecting, documenting, and recording events that meet the definition of an AE or SAE. The Investigator remains responsible for following up AEs that are serious or that caused the participant to discontinue the study intervention as specified in [Section 8.3.3](#).

Requests for follow-up will usually be made via the Study Monitor, although in exceptional circumstances the global patient safety department may contact the Investigator directly to obtain further information or to discuss the event.

8.3.1

Time Period and Frequency for Collecting Adverse Event and Serious Adverse Event Information

- All AEs will be collected from the signing of the ICF until 90 days as specified in the SoA.
- All SAEs will be collected from the signing of the ICF until 90 days of last dose of the study treatment at the time points specified in the SoA ([Table 1](#)). Beyond this reporting period, any new unsolicited SAEs that the Investigator spontaneously reports to the Sponsor will be collected and processed.

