15.2 Adverse Events

Treatment-emergent adverse events (TEAE) are those events with onset or worsening (seriousness or severity) dates occurring within the on-treatment periods as defined in Section 9.7.

For immune-related AEs, an extended period of up to 90 days after last treatment is considered for analyses dedicated to irAEs. PTs belonging to irAEs will be considered as treatment-emergent up to 90 days for dedicated irAE analyses and up to 30 days for general AE analyses.

This includes also AEs ongoing at baseline, which first improve under study intervention and then worsen irrespective of baseline. Adverse events with changes in toxicity grade/severity, seriousness or outcome of AEs are recorded as separate entries in the eCRF with associated end and start dates. Records of the same AE will be considered as one event in the analysis. If the severity of the reported event worsens after start of treatment, the TEAE flag will be re-evaluated for the worse and the subsequent records as per the TEAE definition. If the worse record starts outside of the on-treatment period, it will not appear on the summaries/listings of TEAEs, unless otherwise specified. These events will be kept as separate records in the database in order to maintain the full detailed history of the events. The overall outcome of the adverse event is the

outcome of the last event in the sequence. When such AEs are listed, start, end date and outcome should be provided together with change date, toxicity grade/severity and seriousness per episode.

Adverse events related to study intervention are those events with relationship missing, unknown or yes.

Immune-Related Adverse Events (irAE) are identified according to the methodology outlined in Appendix 1 for a pre-specified search list of MedDRA PTs, documented in the Benefit Risk Strategy Document. Prior to DB lock these events are identified according to a pre-specified search list of MedDRA PTs, documented in a version-controlled repository maintained by the Sponsor and based on medical assessment prior to analysis of the current study. Details are included in Appendix 1.

Infusion-Related Reactions (IRR) are identified based on a list of MedDRA PTs. The detailed criteria of the timing relationship to infusions are specified in [Table 1](#) of Appendix 1.

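### The 90-day safety call may be made as early as day 85, so scheduled AE questioning can stop up to 5 days before the 90-day AE/SAE collection period and irAE analysis window end

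*Protocol*

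**What the plan says.** **Timing of the last AE contact.** Protocol 1.3, Table 1, heads the second Safety Follow-up column "Phone Call 90 Days After Last Treatment (\pm 5 days", a symmetric tolerance of 5 days. The AE row reads "Documentation of AEs X X X X X". The five marks fall under the Eligibility Visit, Treatment Phase, End of Treatment, the 30-day visit and the 90-day call. The sixth column, Long-term Follow-up, is empty. The overall-survival row of the same table does carry a mark there, so the blank appears to be real and not a layout artefact.

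**Length of the period.** The Synopsis (Protocol 1.1) states "Safety Follow-up will continue until 90 days after the last dose of bintrafusp alfa". Protocol 8.3.1 states "All AEs will be collected from the signing of the ICF until 90 days as specified in the SoA" and, for serious events, "All SAEs will be collected from the signing of the ICF until 90 days of last dose of the study treatment at the time points" given in Table 1.

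**Analysis windows.** SAP 15.2 states "For immune-related AEs, an extended period of up to 90 days after last treatment is considered for analyses dedicated to irAEs". Preferred terms classed as irAEs count as treatment-emergent "up to 90 days for dedicated irAE analyses and up to 30 days for general AE analyses".

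**A different label.** Protocol 8.2 states "Ongoing events at the 12-week Safety Follow-up visit should continue to be monitored and documented until resolution or resolution with sequelae". Table 1 has no 12-week Safety Follow-up contact.

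**The concern.** A symmetric tolerance does little harm when a later contact asks the same question. The 30-day visit has the same 5-day tolerance, but the 90-day call follows it and documents AEs again. The 90-day call has no such successor, because Table 1 schedules no AE documentation after it. Protocol 8.3.1 refers back to Table 1 for its time points, so it adds no contact of its own.

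A participant called on day 85 has therefore complied with the schedule, yet nothing scheduled asks about days 86 to 90. In the dedicated irAE tables that participant would still be counted as observed for the full 90 days. An irAE that began after the call and did not reach the site by another route would be missing from the numerator and would not show as missing data. Long-term safety is the purpose of this study, and Protocol 2.3.1 lists irAEs as an important identified risk.

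**Working it through.** The documents give no figure for this gap, so there is none to reproduce. The check is calendar arithmetic.

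**Inputs**
- Permitted call days: 90 − 5 = 85 to 90 + 5 = 95, which is 11 days (Protocol Table 1).
- End of AE/SAE collection: day 90 (Protocol 1.1 and 8.3.1).
- End of the dedicated irAE window: day 90. End of the general AE window: day 30 (SAP 15.2).
- Later contacts: every 12 weeks, plus or minus 2 weeks, with AE documentation not marked (Protocol Table 1).
- Expected enrolment: at least 10 participants (Protocol 1.1).

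**1. Days without scheduled questioning.** Uncovered days = max(0, 90 − call day).

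| Call day | Uncovered days |
|---|---|
| 85 | 5 |
| 86 | 4 |
| 87 | 3 |
| 88 | 2 |
| 89 | 1 |
| 90 to 95 | 0 |

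The maximum is 5 days. That is 5/90 = 5.6% of the 90-day window, and 5/60 = 8.3% of days 31 to 90, the part of the window that only the irAE analyses use.

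**2. Average loss.** The distribution of call dates is not in the documents and has to be assumed. With calls evenly spread over days 85 to 95:
- Share called before day 90: 5/11 = 45%.
- Mean uncovered time: (5 + 4 + 3 + 2 + 1)/11 = 15/11 = 1.36 days.
- As a share of days 31 to 90: 1.36/60 = 2.3%.
- For 10 participants: 10 × 1.36 = about 14 participant-days.

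If calls instead cluster normally around day 90 and are rounded to whole days, the share called early is Φ(−0.5/SD). This is Φ(−0.33) = 37% for an SD of 1.5 days and Φ(−0.20) = 42% for an SD of 2.5 days.

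**3. Next scheduled contact.** Counting the Long-term Follow-up interval from a day-85 call, 85 + 84 ± 14 gives days 155 to 183. Any retrospective mention of a day 86 to 90 event would come at least 155 − 90 = 65 days after that period.

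**4. Outputs exposed.** The primary endpoint in SAP 15.1.1 is tabulated from TEAEs. Protocol 9.4.2 ends the on-treatment period no later than 30 days after the last dose, and SAP 15.2 uses 30 days for general AE analyses. Day 30 comes well before day 85, so those tables cannot change. What remains is the dedicated irAE tables (SAP 15.3.3) and the listings of all AEs, which include events outside the on-treatment period.

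**5. The 12-week label.** 12 × 7 = 84 days, 6 days short of 90 and one day before the earliest call that Table 1 permits.

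**6. After the change.** With a window of 0 to +5 or 0 to +10 days, max(0, 90 − call day) = 0 on every permitted day.

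**The case against.** The best reply is that a call window is a visit tolerance and does not define the collection period. Protocol 8.3.1 runs that period to day 90 whatever the call date, so an event on days 86 to 90 that the site hears about is still reportable. This stands. A reader might infer that AE collection closes at the call, or that only unsolicited SAEs can still arrive in those days. The documents support neither. The sentence on unsolicited SAEs in 8.3.1 applies after the reporting period, not inside it. What can end early is scheduled, solicited questioning.

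Second, Protocol 8.3.2 has participants asked at each study visit about changes in their condition, and the note to the AE row mentions Long-term Follow-up contacts. A later call might therefore recover a missed event. This stands in part. The note deals with holding those contacts by telephone, the AE cell for that column is empty, and the recall would be over about two months or more.

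Third, the effect is very small, and the output is descriptive with no decision rule attached. This stands. SAP 15.2 counts each participant once per category, and the analysis starts from the first dose in the parent study. A percentage changes only if the first event in a category, or a new worst grade, begins in those few days and stays unknown to the site.

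Fourth, part of the irAE window cannot be checked. Protocol 9.4.2 cuts the on-treatment period at the start of subsequent anticancer drug therapy. SAP 9.7 and Appendix 1 are not visible, so it is unknown whether the same cut applies to the 90-day irAE window. If it does, the gap does not matter in the irAE tables for anyone already on new therapy.

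**Conclusion.** The point holds as a minor one. Table 1 allows scheduled AE questioning to end 1 to 5 days before the 90-day collection period and the 90-day irAE window end, and no later contact is scheduled to document AEs. The average loss is about 1.4 days per participant if calls are evenly spread; that spread is an assumption. The 5-day maximum follows from Table 1 alone. Any error lowers irAE counts or leaves listings incomplete, and none can raise them. At 10 participants one missed person is 10 percentage points of the total, but such a miss is unlikely given how short the gap is.

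Three stronger readings should be avoided:
- A reader might infer that the primary safety result is biased. It is not, because its tables use the 30-day window.
- A reader might infer a 6-day gap from the 12-week label. Day 84 lies outside the window in Table 1, and the sentence in Protocol 8.2 concerns following events that are already ongoing. It does not set when questioning about new events ends. It is a separate inconsistency in wording.
- A reader might infer that the 90-day window was chosen in order to capture late irAEs. SAP 15.2 gives no reason for the extension.

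**What to change.** In Protocol Table 1, make the window of the 90-day Safety Follow-up call one-sided: 0 to +5 days, or 0 to +10 days if the present width is to be kept. State that the call asks about AEs through day 90.

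Separately, reconcile the 12-week Safety Follow-up visit named in Protocol 8.2 with the 90-day contact in Table 1.

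Both changes can go into the next amendment and need no extra calls or visits. With 0 to +5 the permitted window falls from 11 days to 6, so slightly more calls may fall outside it. With 0 to +10 the width stays at 11 days, but calls may be made up to 5 days later than now.
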